#### *7.1.1 Investigator Experience*

In accordance to ISO 14155: 2011, the clinical investigator in this study will be:

- An appropriately qualified practitioner legally entitled to practice
- Experienced in the field of application and trained in the use of the device under consideration
- Familiar with the background and requirements of the clinical study methodology, and
- Trained in the proper method of obtaining informed consent

#### *7.1.2 Specific Responsibilities*

The principal investigators and their co-investigator(s) are responsible for the following:

- Subject well-being
- Strictly adhering to the Protocol which includes all testing and follow-up requirements
- Providing the subject with comprehensive information about the study and documenting subject consent and data during the study
- Addressing medical questions that might be asked, either by Axonics or by external Regulatory Agencies, during or after the study
- Notifying Axonics of any deviation from the Protocol with an explanation for the deviation. This notice shall be given as soon as possible, but in a timely manner after the deviation occurred.

Axonics will review and classify all deviations from the Protocol

In case several co-investigators are taking over certain responsibilities, the principal investigator remains responsible for the proper conduct of the clinical study. Axonics must approve co-investigators before taking over responsibilities. The study is not transferable to other centers attended by the investigator unless prior approval is obtained from the appropriate IRB/EC and Axonics.

In addition to certain other documents, an Investigator Agreement must be executed by the parties before subjects are enrolled into the study.

## 7.2 Sponsor Responsibilities

Axonics will serve as the sponsor of this clinical study and takes responsibility and assumes liability for the initiation of the study; however, Axonics does not actually conduct the study.

Axonics will ensure proper monitoring of the study and that all clinical requirements are met.

In addition, Axonics representatives may participate in the conduct of the trial to the extent described in the following section 7.2.1.

In this study, Axonics personnel are not blinded to the study results. Participation in the study will be limited to Axonics personnel who are appropriately qualified and trained. All Axonics personnel will be trained on the appropriate clinical study regulations and guidelines for medical device trials.

It is the responsibility of Axonics to ensure appropriate training regarding the Axonics equipment and study protocol procedures of all individuals involved in the ARTISAN-SNM trial. This includes investigators and other health care professionals at the investigational sites, Axonics personnel, and contractors, if applicable.

### 7.2.1 Role of Axonics Representatives

Axonics personnel will provide support to the health care professionals involved in the study as needed during implant, device programming, and follow-up visits.

Support may include device programming, training, answering questions, or assisting with the operation of the Axonics equipment or the procedures and forms related to the Protocol.

While under the supervision of the clinical investigator, Axonics personnel may operate Axonics SNM equipment during implant or follow-up visits and interact with subjects to accomplish necessary activities. Typical tasks may include:

- Interrogating the device or programming device parameters to physician requested settings
- Clarifying device behavior, operation or diagnostic output as requested by the clinical investigator or other health care personnel
- Entering data on study worksheets, if applicable. This applies to technical data collected during the study procedures or data that is entered into the programmer as long as the responsible clinician verifies and signs the completed worksheet. Worksheets may be used to capture data prior to entry into the EDC system. Medical assessments shall only be completed and signed by a physician.

In addition, Axonics personnel can perform certain activities to ensure study quality. These activities may include:

- Observing testing or medical procedures relevant to Protocol compliance or device function
- Reviewing collected data and study documentation for completeness and accuracy
- Performing source data verification when that individual was not directly involved in the collection of the data under review

Axonics personnel will not:

- Practice medicine
- Provide medical advice, diagnosis or treatment to subjects
- Discuss a subject's condition or treatment with a subject without the approval and presence of a clinician
- Independently collect critical study data or enter data into the electronic database

### **7.3 Insurance**

Axonics will obtain insurance to adequately cover costs in the event of clinical-investigation related injuries.

### **7.4 Monitoring**

Study monitors are individuals who are designated to oversee the progress of a clinical study. They are appropriately trained and qualified to monitor a clinical study.

#### *7.4.1 Monitoring Visits*

Prior to initiating enrolling any subjects, Axonics personnel will confirm that the investigator understands and accepts the obligation to conduct the research study according to the Protocol and applicable regulations and his/her staff have sufficient subjects, time and facilities to conduct the study.

Monitoring will be performed during the study to ensure that compliance with the Protocol and applicable regulations is maintained, that data are collected in a timely, accurate and complete manner, and that the investigator continues to have sufficient staff and facilities to conduct the study safely and effectively. During the monitoring visits, the monitor may review case report forms for timeliness, adequacy, and accuracy and compare to source documents. The monitor may also check the study binder. A final monitoring visit will be conducted before study closure. This final visit will ensure that any pending study issues are resolved. In order to ensure effective monitoring, the investigator must permit the monitor direct access to the case report forms and clinical records.

Additional monitoring details will be described in a separate monitoring plan.

#### *7.4.2 Review of Submitted Data*

The eCRFs submitted by the investigators will also be reviewed by Axonics personnel or designates. The following activities will occur:

- All case report forms will be reviewed for completeness and accuracy upon receipt at Axonics or after entry into the electronic data capture system.
- The site staff and/or the assigned Axonics personnel will be contacted regarding any missing or unclear data.
- Study data will be analyzed by Axonics or delegates and may be transferred to locations outside of the United States and/or be sent to the FDA or any other worldwide regulatory authority in support of a market-approval application.

### **7.5 Independent Data Safety Monitoring Board (DSMB)**

To ensure subject safety, qualified physicians, not otherwise engaged in the study, will from time to time, convene either in person or via teleconference to discuss the conduct of the study from the standpoint of subject safety.

The DSMB will be composed of three (3) physicians: a chairman and two additional physicians.

The DSMB will review the aggregate safety data and evaluate any safety issues that may arise during the conduct of study.

The DSMB will review and adjudicate individual adverse events.

The DSMB Charter will describe further details of the DSMB activities.

## 8 REGULATORY AND COMPLIANCE REQUIREMENTS

### 8.1 Statement of Compliance

The study will be conducted according to the stipulations of the Declaration of Helsinki, ISO 14155:2011 and all other applicable regulations as determined by the US FDA.

### 8.2 Informed Consent

Informed Consent is mandatory from all subjects prior to the subject's participation in the study. Axonics will provide the Informed Consent template to investigators participating in this study.

The process of obtaining Informed Consent shall comply with the Declaration of Helsinki, ISO 14155:2011 and applicable national regulations (local IRBs/ECs and/or Regulatory body, as applicable).

The process of obtaining informed consent shall:

- avoid any coercion of or undue influence of subjects to participate
- not waive or appear to waive subject's legal rights
- use native language that is non-technical and understandable to the subject
- provide ample time for the subject to consider participation and ask questions
- be personally signed and dated by the subject and the investigator

It is the investigator's sole responsibility to have the original signed Informed Consent retained on file and a copy given to the subject.

### 8.3 Subject Data Confidentiality

Throughout the study, subject confidentiality shall be observed at all times by all parties involved, including in reports and publications. All data will be secured and stored according to country-specific requirements.

The participating sites shall ensure that data (e.g. worksheets, files, programmer printouts, etc.) forwarded to Axonics does not contain any subject identifying data (such as name, birth date, etc.) other than the subject ID.

Only authorized Axonics personnel or designated representatives will have access to these confidential files. Subject data may be made available to foreign Regulatory Agencies, Health or other Governmental Authorities, but under strict confidentiality.

### 8.4 Control of the Study Devices and Equipment

Axonics will control the availability of the Axonics SNM System and ship products only to Axonics representatives or study investigators.

Axonics will keep records that indicate the destination and date of shipment.

The disposition of all devices will be tracked. Upon request, unused devices must be returned to Axonics.

## 8.5 Out-of-Service Product

Any implantable product (such as a Neurostimulator or Tined Lead) that has been removed from a subject is considered an out-of-service product. For example, out-of-service product shall include explanted product and devices that do not function appropriately at time of implant. Any out-of-service product should be returned to the Sponsor for analysis. In the event of a subject death, every effort should also be made to retrieve and return product to the Sponsor.

## 8.6 Adverse Events

All Adverse Events reported to the Sponsor during the study will be reviewed and adequately reported and classified to comply with applicable regulations (ISO 14155:2011) and vigilance requirements.

Investigators will be asked to classify whether an adverse event is considered serious or non-serious and whether it is considered device or procedure related.

Axonics will determine whether a reported Adverse Event is anticipated or unanticipated.

### 8.6.1 Adverse Event Classification

**Adverse Event (AE)** – any untoward medical occurrence, unintended disease or injury, or untoward clinical signs (including abnormal laboratory findings) in subjects, users or other persons, whether or not related to the investigational medical device. This definition includes events related to any procedure in the protocol. The following are NOT considered AEs:

1. Any event expected to occur during the normal course of treatment that is not untoward.
2. Usual aches and pains following the surgical implant procedure. (Pain that is unusually intense or prolonged may be an AE.)
3. Unusual or uncomfortable sensations during the programming of the device or when the Remote Control is used to change stimulation settings. These occurrences are part of the usual standard of care. If the sensation is not resolved by reprogramming then the event may be considered an AE.
4. Change in the effectiveness of the SNM therapy may change over time, possibly requiring changes in programming parameters.
5. Underlying diseases, recorded at baseline, unless there is an increase in severity or frequency during the course of the investigation.
6. Death should not be recorded as an AE, but should only be reflected as an outcome of a specific SAE.

Any AE experienced by the study subject after informed consent, whether before, during or subsequent to the procedure, must be recorded in the eCRF.

**Adverse Device Effect (ADE)** – adverse event related to the use of an investigational medical device.

- a) This definition includes adverse events resulting from insufficient or inadequate instructions for use, deployment, implantation, installation, or operation, or any malfunction of the

investigational medical device.

- b) This definition includes any event resulting from use error or from intentional misuse of the investigational medical device.

**Serious Adverse Device Effect (SADE)** – An effect that has resulted in any of the consequences characteristic of a serious adverse event related directly to the investigational medical device.

**Serious Adverse Event (SAE)** – adverse event that:

1. Led to death
2. Led to serious deterioration in the health that either resulted in
  - a. a life-threatening illness or injury, or
  - b. a permanent impairment of a body structure or a body function, or
  - c. In-patient or prolonged hospitalization, or
  - d. medical or surgical intervention to prevent life-threatening illness or injury or permanent impairment to a body structure or a body function,
3. Led to fetal distress, fetal death or a congenital abnormality or birth defect

NOTE 1: This includes device deficiencies that might have led to a serious adverse event if a) suitable action had not been taken or b) intervention had not been made or c) if circumstances had been less fortunate.

NOTE 2: Hospitalization for a pre-existing condition, or a procedure required by the protocol, without serious deterioration in health, is not considered a serious adverse event.

**Unanticipated Adverse Device Effect (UADE)** - Any serious adverse effect on health or safety or any life-threatening problem or death caused by, or associated with, a device, if that effect, problem, or death was not previously identified in nature, severity, or degree of incidence in the clinical trial protocol or application (including a supplementary plan or application), or any other unanticipated serious problem associated with a device that relates to the rights, safety, or welfare of subjects.

NOTE: Anticipated serious adverse device effect (ASADE) is an effect, which by its nature, incidence, severity or outcome has been identified in the risk analysis report.

**Device Deficiency** - inadequacy of a medical device related to its identity, quality, durability, reliability, safety or performance, such as malfunction, misuse or use error or inadequate labeling.

**Malfunction** - failure of an investigational medical device to perform in accordance with its intended purpose when used in accordance with the instructions for use.

### 8.7 Relationship to Study Device(s)

The Investigator must assess the relationship of the AE to the study device as related or unrelated. See criteria in Table 3.

Table 3: Criteria for Assessing Relationship of Study Device to Adverse Event

Classification	Description
Unrelated	The adverse event is determined to be due to a concurrent illness or other effect that is not related to the investigational device.
Related	The adverse event is determined to be potentially related to the investigational product, and an alternative etiology is equally or less likely compared to the potential relationship to investigational product, or There is a strong relationship to investigational product, or recurs on re-challenge, and another etiology is unlikely, or There is no other reasonable explanation for the event.

### 8.8 Relationship to Study Procedure

The Investigator must assess the relationship of the AE to the study procedure as related or unrelated. See criteria in Table 4.

Table 4: Criteria for Assessing Relationship of Study Procedure to Adverse Event

Classification	Description
Unrelated	The adverse event is determined to be due to a concurrent illness or other effect that is not related to the study procedure.
Related	The adverse event is determined to be potentially related to the study procedure, and an alternative etiology is equally or less likely compared to the potential relationship to study procedure, or There is a strong relationship to study procedure, or recurs on re-challenge, and another etiology is unlikely, or There is no other reasonable explanation for the event.

### 8.9 Pain-related Adverse Events

Adverse events associated with pain should be consistently assessed and classified across Investigators. The following guidance should be followed in assessing pain-related adverse events:

- All device-related AEs associated with pain should be assessed on a numeric rating scale. The subject should be asked to rate his or her pain in the last 24 hours from 0 to 10 (11-point scale) with the understanding that 0 is equal to “no pain” and 10 is equal to “worst possible pain.”
- Pain encountered within thirty (30) days of the implant procedure that is associated with the lead or Neurostimulator implant sites should be considered as procedure-related pain and not as device-related pain.
- Pain encountered after thirty (30) days post-implant that is associated with the

Neurostimulator implant site should be classified as follows:

- Transient Lead site pain: pain at the lead implant site that persists for less than thirty (30) days and is resolved without surgical intervention,
- Persistent Lead site pain: pain at the lead implant site that persists for thirty (30) or more days or any lead implant site pain requiring surgical intervention.
- Transient Neurostimulator site pain: pain at the Neurostimulator site that persists for less than thirty (30) days and is resolved without surgical intervention,
- Persistent Neurostimulator site pain: pain at the Neurostimulator site that persists for thirty (30) or more days or any Neurostimulator pain requiring surgical intervention.

#### **8.10 Tined Lead Migration**

Tined lead migration is an adverse event often reported in sacral neuromodulation studies. To standardize the reporting of lead migration events this study will utilize imaging to assess lead migration. If a patient has an unexpected loss of efficacy or emergence of pain or discomfort associated with their implant that cannot be resolved with reprogramming, an x-ray or fluoroscopic image of the lead may be acquired to assess whether or not the lead has migrated. Criteria for confirming migration include:

- The ability to produce and compare images of the lead location at the implant procedure and at a timepoint following report of the unwanted outcome (loss of efficacy or discomfort)
- Clear evidence on the images that the lead has been displaced at least 2 cm from the initial lead placement position

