### *3.4.1 Implanted Lead Issues*

In the event that the implanted Tined Lead fails, migrates, or is implanted in an undesired position such that adequate therapy cannot be provided, Axonics recommends revising or replacing the lead. Tined Lead revision and replacement does not require a Neurostimulator replacement, however, the physician has the option to replace the Neurostimulator at that time. If the subject does not wish to undergo a replacement in the case of lead failure, their device should be deactivated. If a Tined Lead replacement occurs, the original activation date shall remain as Day 0.

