#### *4.1.2 Implant*

A qualified physician who has been trained on the Axonics SNM System implantation must perform the implant. In the absence of specific guidance from Axonics on surgical procedures (such as anesthesia, surgical cut-down, post-operative wound care), the physician should follow their usual standard of care.

The following are requirements of the study protocol:

- Subjects must use an antiseptic wash the night before surgery.
- Appropriate intravenous antibiotics must be administered at the time of the surgical procedure.
- Surgical procedure will be performed under general anesthesia, conscious sedation, or MAC anesthesia. Use of muscle relaxants should be avoided to allow for observation of intraoperative motor responses.
- Lead impedance measurements must be obtained and recorded at the time of implant to verify system integrity. Impedances should be within 400 to 6000 ohms. Physicians should refer to the Clinician Programmer Manual for information on troubleshooting impedances that are not within range.
- Intra-operative testing must be performed. Stimulation must evoke motor responses consistent with the S3 sacral nerve at motor thresholds less than 4mA on at least two (2) electrodes to confirm acceptable Tined Lead placement and proceed with the Neurostimulator implant. Motor threshold is defined as the lowest stimulation amplitude that provides a clear anal bellows with or without big toe flexion. Sensory threshold is defined as the lowest stimulation amplitude that provides a feeling of “tapping”, “pulling” or “tingling” in the rectum, extending forward to scrotum or vagina and/or labia. Subjects who do not provide a positive motor response to intra-operative testing will be managed according to Section 3.3.3.
- Tined Lead placement must be verified with lateral and anterior-posterior fluoroscopy. The lead must be in the S3 (preferred) or S4 foramen. An image of the lateral fluoroscopy showing the position of the tined lead must be captured and maintained by the site.
- Neurostimulator implanted no deeper than 3.0 cm below the skin.
- Neurostimulator implanted horizontally with the ceramic side farthest from the midline.
- Wound should be irrigated prior to closure.

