### *5.2.4 Analysis methods*

#### *5.2.4.1 Primary Endpoint*

The primary effectiveness endpoint is that the proportion of all implanted subjects that are Treatment Responders is greater than 50% at 6-months post-activation. If the proportion of Treatment Responders is statistically greater than 50%, the study will be considered to be a success.

As mentioned above, a secondary endpoint analysis will also be conducted in subjects who are "Trial Responders" to allow for a direct comparison to the published SNM literature where analysis at follow-up visits are performed only in trial responders i.e. subjects that have  $\geq 50\%$  improvement in

symptoms after a one-month trial with an external stimulator.

The primary endpoint will be tested for significance based on a one-sided binomial test (such as Fisher's exact test) at a 2.1% significance level to account for two additional early looks as detailed in the Statistical Analysis Plan.

The primary safety endpoint of the study is the rate of adverse events (AEs) through 6-months.

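### A painless loss of efficacy that ends in uncomplicated lead revision may be recorded with no adverse event, and no revision rate is tabulated to show it

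*Combined protocol and SAP*

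**What the plan says.** - **Endpoint.** Section 5.2.4.1: "The primary safety endpoint of the study is the rate of adverse events (AEs) through 6-months". It carries no hypothesis and no performance goal. Section 1.4 lists the categories to be tabulated: device effects, procedure effects, serious events, serious device effects and unanticipated device effects. Revision, replacement and explant are not among them.
- **What is not an AE.** Section 8.6.1 lists six exclusions. Item 4 reads: "Change in the effectiveness of the SNM therapy may change over time, possibly requiring changes in programming parameters". Item 3, on uncomfortable sensations, adds that the event may become an AE if reprogramming does not resolve it. Item 4 adds nothing of the kind.
- **Migration.** Section 8.10 sets out to standardise migration reporting through imaging. If efficacy is lost or discomfort appears and reprogramming does not help, "an x-ray or fluoroscopic image of the lead may be acquired to assess whether or not the lead has migrated". The text continues with "Criteria for confirming migration include" and gives two items: the ability to "produce and compare images of the lead location at the implant procedure and at a timepoint following report" of the unwanted outcome, and "Clear evidence on the images that the lead has been displaced at least 2 cm from the initial lead placement position".
- **Reference image.** Section 4.1.2: "An image of the lateral fluoroscopy showing the position of the tined lead must be captured and maintained by the site".
- **Re-operation.** Section 3.4.1 covers a lead that fails, migrates or is badly placed "such that adequate therapy cannot be provided, Axonics recommends revising or replacing the lead". Day 0 does not move after a lead replacement.

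**The concern.** A second operation on the lead is one of the main harms that an implanted system can cause. Under the present wording, whether it appears in the safety results can depend on two site-level choices: whether to take a follow-up image, and whether to read item 4 as covering a loss of efficacy that reprogramming could not correct. Two sites could record the same clinical course differently, although Section 8.10 aims at uniform reporting. With no revision rate in Section 1.4, a reader of the results could not see how many subjects were operated on again. The study is a pivotal pre-market study, and Section 1.1 hypothesises that the device's improvements may reduce adverse events. A complete count of re-operations is needed to judge that.

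**Working it through.** The documents give no expected AE, migration or revision rate, so there is no planned figure to reproduce. The check follows one subject through the rules and then sets a scale.

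**Step 1. Follow the subject.** A subject loses efficacy without pain. Reprogramming fails. No follow-up image is taken, or the image shows less than 2 cm. The lead is revised or replaced without complication.

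- *Section 8.10:* not a confirmed migration, because one or both criteria are unmet. No other route to confirmation and no suspected category is given.
- *Section 8.6.1, item 4:* the change in effectiveness is on the excluded list. Its text mentions programming changes and is silent on surgery. Item 3 shows that the authors knew how to write an exception for failed reprogramming; item 4 has none.
- *Section 8.6.1, serious events:* the event must first be an AE. The surgical clause is also limited to preventing life-threatening illness or injury or permanent impairment.
- *Section 8.13:* a device deficiency is kept out of AE reporting unless it leads to an AE, which returns the question to item 4.
- *Section 8.9:* the pain rules do not apply to a painless case.
- *Section 1.4:* no row counts the operation itself.
- *Section 5.2.4.6.1:* explant, or withdrawal for an adverse event or lack of efficacy, is treated as failure. Lead revision is not named and Day 0 is unchanged, so the effectiveness analysis need not flag the subject either.

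Result: the subject can have zero AEs through 6 months without any rule being broken.

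**Step 2. Ceiling per subject.** Taking the 116 implanted subjects of Section 5.2.2 as the denominator:

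1/116 = 0.0086, or 0.86 percentage points of the subject-level AE rate.

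Three such subjects give 3/116 = 2.6 points, and six give 6/116 = 5.2 points. These are ceilings, because a subject with any other AE, related or not, is already counted. Section 5.2.3.1 also adds intraoperative screen failures to the safety set, which makes each share slightly smaller.

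**Step 3. Illustration on assumed rates.** Let p be the proportion revised for lost efficacy by month 6 and f the share of those left unrecorded. Both are my assumptions. Expected number unrecorded = 116 × p × f. Chance of at least one = 1 − (1 − p × f)^116.

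| p | f | Expected unrecorded | Chance of at least one |
|---|---|---|---|
| 2% | 25% | 0.6 | 44% |
| 2% | 50% | 1.2 | 69% |
| 5% | 50% | 2.9 | 95% |
| 10% | 50% | 5.8 | 99.7% |
| 10% | 100% | 11.6 | nearly 100% |

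The table shows only how the size moves with the assumptions. It does not estimate what will happen.

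**The case against.** The strongest reply is that AE status and the migration label are separate. Section 8.10 decides only when migration is confirmed; missing the 2 cm mark does not turn the complaint into a non-event. The AE definition in Section 8.6.1 is broad, and an investigator may well report a second operation under it. Item 4 speaks of programming changes and can be read as limited to them. Other routes also catch much of this:

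- pain needing surgery (Section 8.9);
- AEs that follow from a deficiency (Section 8.13);
- AEs from malfunction or inadequate implantation instructions (the device-effect definition);
- deficiencies that might have become serious without intervention (the first note to the serious-event definition).

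Removed leads should be returned for analysis (Section 8.5), so replacements leave a trace. Section 8.10 says that its criteria include the two items, which is not literally exclusive. The separate analysis plan and the DSMB Charter, to which the protocol defers, might hold a revision table.

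Most of this stands, and it narrows the point to painless, uncomplicated revisions that an investigator does not report. It does not close the gap. Item 4 remains ambiguous beside item 3, independent adjudication acts on events that have been reported, and Section 1.4 still lists no revision rate.

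Four stronger readings are tempting and are not supported:

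- *The protocol requires these cases to be left out.* It allows the omission; nothing orders it.
- *The trial compares safety with the marketed device.* It is single-arm, with subjects as their own controls (Section 1.6). The statements in Sections 1.2 and 6.2 that Axonics outcomes resemble those of the marketed device rest on an earlier study.
- *Some 2 to 12 operations will go uncounted.* That needs a 2–10% revision rate, which the documents do not give, and every revision unreported.
- *Both implant views should have been kept.* Nothing shows that the lateral view is inadequate, and Section 5.2.2 says all subjects were already implanted by Rev F, so such a rule could not act.

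**Conclusion.** The point holds in a limited form. Sections 8.6.1 (item 4), 8.10, 8.13 and 3.4.1, read together, permit a painless loss of efficacy that ends in uncomplicated lead revision or replacement to be recorded with no AE, and Section 1.4 has no count that would reveal it. The consequence is possible under-counting in a descriptive primary safety rate; no success decision depends on it. The size is at most about 0.86 points per such subject, assuming a denominator of 116 and no other AE in that subject. How many subjects are affected cannot be derived from the documents. It is worth correcting because the rule acts on the primary safety measure and the correction is cheap.

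**What to change.** Reconcile Sections 8.6.1, 8.10, 8.13 and 3.4.1:

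1. In Section 8.6.1, limit item 4 to changes in effectiveness managed by reprogramming. State that any loss of efficacy leading to surgical revision, replacement or explant is recorded as an AE, whatever the imaging shows.
2. In Section 8.10, keep the present criteria for confirmed migration and report suspected but unconfirmed cases beside them.
3. In Section 1.4, add a tabulated rate of surgical revision, replacement and explant through 6 months, in all implanted subjects.

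Because every subject was implanted by Rev F, apply these rules uniformly to all implanted subjects from existing records. Device disposition is tracked (Section 8.4) and removed product should be returned (Section 8.5). State in the report how many events the re-review added, since the AE rule is being clarified during follow-up. These are recording and reporting rules only; they call for no added imaging and no change in when a lead is revised.

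Cost: protocol and case report form wording, extra rows in the safety tables, and a second review of some earlier records. The reported AE rate may rise slightly.
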